##### MRI:

- The proportion of subjects demonstrating a decrease in Liver percent fat by MRI at 24 weeks compared to baseline equal greater than 5% compared to placebo
- The proportion of subjects demonstrating a decrease in Liver percent fat by MRI at 24 weeks compared to baseline equal greater than 10% compared to placebo

**Exploratory endpoints:**

- Mean serum concentrations of: LPS, CK-18 fragments and adiponectin and subsets of cytokines IL6, IL-1 $\alpha$ , IL1 $\beta$ , IL-2, IL-3, IL-4 IL-10, IL-13, IL-12, IL-17 $\alpha$ , IL-23, IFN $\gamma$  TGF $\beta$  and TNF $\alpha$
- Serum metabolomics
- Relative levels of regulatory T cells in PBMC samples, including CD4, CD8, CD25, FoxP3, NKT and CD62
- Characterization of the gut microbiome.
- Explore a dose effect

## 5. STUDY DESIGN

### 5.1 Study Design

This is a randomized, double blind, placebo controlled, 3-arm parallel group, multi-dose, multi-center study

### 5.2 Dosing Regimens

There are 3 regimens in this study as described in [Table 2](#) below.

**Table 2: IMM-124E daily dose levels**

Treatment arm	IMM-124E Dose
A	600mg three times daily
B	1200mg three times daily
C	matching placebo only, three times daily

At least 40 subjects will be enrolled into each cohort. For each subject, the 24 week primary treatment period will consist of three times daily oral administration of the allocated IMM-124E dose or matching placebo.

### 5.3 Study Sites

This will be a multicenter study involving approximately 30 clinical study sites.

### 5.4 Estimated Duration of the Study

The recruitment period will be approximately 24 months. The Screening period will be up to 45 days and subjects will receive treatment for 24 weeks. Subjects who withdraw from treatment will be followed for 28 days after treatment cessation, where possible.

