	
 
• Mean serum ALT, aspartate aminotransaminase (AST), bilirubin, albumin and gamma-glutamyl transpeptidase (GGT) at Weeks 4, 8, 12, 16, 20 and 24
 
• Proportion of subjects whose ALT at Week 24 is within the normal reference range defined as <math>\leq 19</math> IU/L for women and <math>\leq 30</math> IU/L for men.
 

Exploratory outcome measures	
 
• Mean serum concentrations of: lipopolysaccharide (LPS), C-reactive protein (CRP), cytokeratin (CK)-18 fragments, glucagon-like peptide (GLP)-1 and adiponectin and subsets of inflammatory cytokines: interleukin (IL)-6, IL-1<math>\alpha</math>, IL1<math>\beta</math>, IL-2, IL-3, IL-4 IL-10, IL-13, IL-12, IL-17<math>\alpha</math>, IL-23 interferon gamma (IFN<math>\gamma</math>), Transforming Growth Factor Beta (TGF-<math>\beta</math>) and tumor necrosis factor alpha (TNF<math>\alpha</math>)
 
• Serum metabolomics
 
• Relative levels of regulatory T cells in peripheral blood mononuclear cells (PBMC) samples, including CD4, CD8, CD25, FoxP3, NKT, CD62 and CD69 T cells;
 
• Characterization of the gut microbiome
 
• Explore a dose effect
 

Study design:	This is a randomized, double blind, placebo controlled, 3-arm parallel group, multi-dose, multi-center study.
Study duration / participant:	Up to 45 days for Screening and 24 weeks of treatment.  Subjects terminating study drug will be followed-up post-treatment for 28 days.
Number of participants:	At least 120, randomized 1:1:1  Treatment allocation will be stratified by the following: 
 
• Baseline MRI Liver Fat, according to the following scale: <math>\leq 10\%</math>, <math>10\% < X \leq 20\%</math>, <math>20\% < X < 30\%</math> and <math>\geq 30\%</math>
 
• Diabetic status defined as being normal (HBA1C <math>\leq 6.0</math>) or diabetic (having a diagnosis of Type II diabetes and/or HBA1C <math>> 6.0</math> and <math>\leq 9.0</math> whether or not receiving allowable medication).
 

Study drug:	IMM-124E 600mg tablet
Control group:	Placebo to match
Dose Regimens	Arm A: IMM-124E 600mg three times daily; Arm B: IMM-124E 1200mg three times daily; Arm C: Matching placebo three times daily.  All treatment dose regimens are administered per orally

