 Including: total cholesterol, triglycerides, HDL and LDL

 Including: hemoglobin, hematocrit, red blood cell (RBC) and RBC morphology, white blood cell (WBC) and differential WBC count, platelet count, mean corpuscular volume (MCV), mean corpuscular hemoglobin concentration (MCHC).

 Serum biomarkers – CK-18, LPS, adiponectin, GLP-1 and cytokines (IL-1 $\alpha$ , IL1 $\beta$ , IL-2, IL-3, IL-4, IL-6, IL-10, IL-13, IL-12, IL-17 $\alpha$ , IL-23, IFN $\gamma$ , TGF- $\beta$  and TNF $\alpha$ )

 PBMC - FACS analysis for CD4 CD8 CD25 FoxP3 NKT CD62 CD69 T cells

 Serology (including HIV, HCV and HBV test) results will be acceptable for eligibility within range of 6 months prior to screening.

 MRI: Baseline MRI to be performed as soon as subject eligibility is determined. Week 24 MRI to be done within +/- 2 weeks week 24.

 Randomization is to be done within 2 weeks post baseline MRI, when the MRI result is available for stratification (hepatic fat fraction form – to be received by central imaging lab).

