### 7.2.9 **Week 24 (or early withdrawal from treatment)**

All subjects will return to the clinic and the following procedures performed and documented

- A targeted physical examination (see [Section 7.3.2](#))
- AE assessment (see [Section 10.2](#))
- Vital signs (blood pressure, temperature, heart rate and respiratory rate) (see [Section 7.3.3](#))
- Measurement of bodyweight and waist and hip circumferences (see [Section 7.3.3](#))
- Concurrent medication recording (see [Section 9](#))
- Study medication accountability (return of all unused medication) (see [Section 8](#))
- Diet and exercise counseling and 7-day diary issue (see [Section 7.3.5](#))
- Administration of the AUDIT questionnaire
- MRI scan (see [Section 7.3.13](#))
- Urine pregnancy test for women of childbearing potential (see [Section 7.3.10](#))
- Collection of blood and serum samples for:
  - Hematology (see [Section 7.3.6](#))
  - Coagulation (see [Section 7.3.6](#))
  - Fasting clinical chemistry (see [Section 7.3.6](#))
  - Fasting lipid analysis, including HOMA-IR (see [Section 7.3.6](#))
  - HBA1C
  - Pharmacokinetics (see [Section 7.3.8](#))
  - PBMCs (see [Section 7.3.9](#)) – at selected sites only
  - Biomarker analysis including CK-18 fragments, LPS, adiponectin, GLP-1 and cytokines (see [Section 7.3.9](#))
  - Serum metabolomics
- Collection of a stool sample for microbiome assessment (see [Section 7.3.11](#)) – selected sites only.

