### 7.2.10 **Week 28 (Post-treatment Follow-up)**

Subjects will return to the clinic 4 weeks after completion of treatment at Week 24 or early withdrawal and the following assessments will be performed:

- A targeted physical examination (see [Section 7.3.2](#))
- AE assessment (see [Section 10.2](#))
- Vital signs (blood pressure, temperature, heart rate and respiratory rate) (see [Section 7.3.3](#))
- Concurrent medication recording (see [Section 9](#))
- Urine pregnancy test for women of childbearing potential (see [Section 7.3.10](#))
- Collection of blood and serum samples for:
  - Hematology (see [Section 7.3.6](#))

- o Coagulation (see [Section 7.3.6](#))
- o Fasting clinical chemistry (see [Section 7.3.6](#))
- o Diet and exercise 7-day diary review (see [Section 7.3.5](#))

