### 11.3 Withdrawal of Subjects from Study drug

[Section 10.6](#) provides guidance for dose discontinuation of Study drug in the event of AEs or abnormal laboratory values. If a subject permanently discontinues study drug, for example as a result of an AE, subjects should be encouraged to continue participation in the study in order to obtain ongoing measurement of study outcomes to minimize missing data. At a minimum, every attempt should be made to continue to follow the subject until resolution of the adverse event. All subjects who discontinue study medication dosing should be followed for at least 28 days after the last dose of Study drug in order to monitor subjects for possible post-treatment events which may occur after Study drug has been discontinued.

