7.2 Primary efficacy analyses

The hepatic fat fraction will be summarised and tabulated for the Baseline and Week 24 visits along with change from Baseline by randomised treatment group. Change in hepatic fat fraction from Baseline will be analysed using analysis of variance on the ITT, PP and FAS populations, where the model will include the treatment group and another subgrouping variable. As determined by baseline values, hepatic fat fraction categories ($\leq 10\%$, $>10\% - <21\%$, $\geq 21\% - <30\%$ and $\geq 30\%$), HbA1c group ($< 6\%$ and $\geq 6\%$), and ALT (greater or less than 1.5 x the upper normal limit) will be used to subgroup the analysis populations. Further, data from liver biopsies up to 6 months prior to screening will also be used to subgroup analysis populations based on fibrosis (0-1 vs. 2-3), NAS inflammation (0-1 vs. 2-3), and NAS ballooning (0-1 vs. 2). These will be used in addition to the main effects factors and the two-way interaction of those main effects.

In the primary analysis, any missing data will remain missing. Treatment effects between placebo and each of the active treatment groups within each of the hepatic fat and HbA1c categories will be generated and tested for significant differences between treatment and placebo using pre-specified contrasts.

To examine the effect of treatment within the various levels of these subgroup variables, a mixed models ANOVA will be employed if there are an appropriate number of observations in each cell (created by the crossing of study treatment and subgroup categories) and the data does not differ significantly from a normal distribution. In the event that this is not the case, the data will be ranked in an attempt to normalise it, and pairwise contrasts between treatment groups will be performed using Wilcoxon rank sum tests within each combination of visit and subgroup variable level will be performed. However, if the ranked data is also not normally distributed, a permutation test will be employed whereby the unranked data will be randomly sampled (Lehmann, 2006). No adjustment for multiple testing will be made. See Appendix 1 for more information on both the Wilcoxon rank-sum test and the permutation test.

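### The schedule replaces the Week 24 MRI with a scan at treatment withdrawal and gives no off-drug path to Week 24, in conflict with Protocol 11.3

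*Protocol*

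**What the plan says.** Protocol 11.3 separates stopping drug from leaving the study. After permanent discontinuation, "subjects should be encouraged to continue participation in the study in order to obtain ongoing measurement of study outcomes to minimize missing data". It also sets a minimum: "All subjects who discontinue study medication dosing should be followed for at least 28 days after the last dose of Study drug".

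The operational sections do not carry this separation through:

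- Synopsis, study duration: "Subjects terminating study drug will be followed-up post-treatment for 28 days".
- Section 5.4: "Subjects who withdraw from treatment will be followed for 28 days after treatment cessation, where possible".
- Section 7.2.9 defines a single visit, "Week 24 (or early withdrawal from treatment"), whose procedures include the MRI. Table 1 matches it with one W24/WD column, which holds the only MRI after Baseline.
- Section 7.2.10: "Subjects will return to the clinic 4 weeks after completion of treatment at Week 24 or early withdrawal". No MRI is listed there.
- Table 1, footnote 7, on timing: "Week 24 MRI to be done within +/- 2 weeks week 24".

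The primary endpoint is change from Baseline in MRI liver fat at Week 24 (Protocol 4.2). The FAS is every dosed subject, analysed as randomised (12.2.1). SAP 7.2 adds: "In the primary analysis, any missing data will remain missing". Multiple imputation is planned only as a sensitivity analysis (SAP 3.3 and 7.2). The SAP has no rule for an MRI taken at early withdrawal.

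**The concern.** A site that follows Table 1 and Section 7.2 will scan a subject when tablets stop, see the subject once more four weeks later, and have no further visit to schedule. The subject may be willing to stay, as 11.3 hopes, but no visit is written for someone who is off drug and still in the study.

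The primary comparison is meant to be as randomised at a fixed time. For subjects who stop early, the endpoint is then one of two things. If it is missing, the FAS estimate describes mainly those who continued. If it is taken from the withdrawal scan, an observation from, say, Week 8, made as drug stops, is pooled with 24-week observations. The documents do not choose between these. If the two doses are tolerated differently, either reading affects the arms unequally, and the study has a secondary objective of recommending a dose.

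**Working it through.** **Timing.** The MRI window is 24 ± 2 weeks, i.e. Week 22 to Week 26 (Table 1, footnote 7). The withdrawal scan falls in the week of stopping (7.2.9). The last visit is that week + 4 (7.2.10).

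| Drug stopped (week) | Withdrawal MRI (week) | In Week 22–26? | Last visit (week; no MRI) |
|---|---|---|---|
| 4 | 4 | no | 8 |
| 8 | 8 | no | 12 |
| 12 | 12 | no | 16 |
| 16 | 16 | no | 20 |
| 20 | 20 | no | 24 |
| 22 | 22 | yes | 26 |

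Before about Week 22 the schedule yields an early scan and none at the primary timepoint. From Week 22 the withdrawal scan serves as a Week 24 scan.

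**The plan's own figure.** Inputs from Protocol 12.1: 40 per arm, difference 5, SD 7.3, two-sided 0.05, unpaired t-test. The SD follows from √(6² + 6² − 2 × 0.25 × 6 × 6) = √54 = 7.35, stated as 7.3. Power is 85.7% by the noncentral t and 86.5% by the normal approximation. The stated figure of about 85% is reproduced.

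**What is estimated.** The documents give no discontinuation rate. Assume a proportion p of 15–20% in the active arm, full loss of benefit in those who stop, and otherwise similar outcomes in stoppers and continuers. The as-randomised effect is then −5 × (1 − p):

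- p = 15%: −5 × 0.85 = −4.25 points
- p = 20%: −5 × 0.80 = −4.0 points

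An analysis of available Week 24 scans would still show about −5. The gap is 0.75 to 1.0 point, and it scales with p and with the share of benefit lost.

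**Why power is not the argument.** On the same assumptions:

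| Analysis | p = 15% | p = 20% |
|---|---|---|
| Stoppers missing and not replaced | n = 34, effect 5: 79.5% | n = 32, effect 5: 76.9% |
| All 40 scanned at Week 24 | effect 4.25: 73.0% | effect 4.0: 67.7% |

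Keeping stoppers in lowers power here, because it estimates the smaller as-randomised effect.

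**The case against.** Four stronger readings are tempting, and the documents do not support them.

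- *The Week 24 MRI is never due after stopping.* It is brought forward, not dropped: 7.2.9 and the W24/WD column require it at withdrawal from treatment, and from Week 22 that scan is in window.
- *The subject is put out of the study after 28 days.* No section says so. The 28 days in 11.3 is a minimum, and 5.4 is an estimate of duration qualified by feasibility. Section 7.4 counts visits from Baseline, so a retained subject has dates to attend. The exit is inferred from the schedule, which gives such a subject no instruction.
- *Early stoppers are dropped as missing.* That is one reading only. SAP 3.2 gives visit windows but does not exclude data outside them, and SAP 9 brings early terminations into the interim population.
- *The trial loses power.* Section 11.5 replaces early withdrawals to reach the planned number of completers, so a fall to 34 or 32 evaluable per arm would require that replacement does not happen.

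It can also be said that the trial is exploratory, that multiple imputation is planned, and that SAP 8.6 examines early terminations separately. These points limit the weight of the concern but do not answer it. Replacement adds completers, not outcomes for those who stopped. Imputation with almost no off-drug Week 24 scans must borrow mainly from continuers. The early-termination summary is descriptive and supplies no Week 24 MRI.

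**Conclusion.** The conflict stands: 11.3 asks for outcome follow-up off drug, while the synopsis, 5.4, 7.2.9, 7.2.10 and Table 1 tie the scan and the last visit to withdrawal from treatment. For subjects who stop before about Week 22, the primary endpoint is either absent or measured early, and the SAP does not say which. Both outcomes depart from an as-randomised Week 24 comparison.

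The timing result follows directly from the protocol. The size does not: −4.25 to −4.0 against −5 depends on an assumed 15–20% discontinuation rate and an assumed full loss of benefit, neither of which is in the documents. With few early stoppers, or with benefit that persists off drug, the gap is smaller. The change should be made because it is cheap and brings the schedule into line with the protocol's own stated aim.

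**What to change.** Reconcile the synopsis, 5.4, 7.2.9, 7.2.10 and the W24/WD column of Table 1 with 11.3:

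1. A subject who stops study drug but has not withdrawn from the study keeps the remaining scheduled outcome visits and has the MRI at Week 24 counted from Baseline.
2. The early MRI is done when a subject withdraws from the study or declines further participation.
3. The 28-day safety contact after the last dose is kept.

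Add one sentence to SAP 7.2: an MRI outside Weeks 22–26 is not counted as the Week 24 value in the primary analysis and is used only in sensitivity analyses. SAP 3.2 gives only ± 3 days for visits at this stage, so the MRI window should be stated there too.

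The cost is a wording amendment. For a subject who stays, the scan is moved rather than added. There are two downsides. Some off-drug visits will take place that would otherwise have been skipped. A subject who stops drug, intends to return and is then lost would have no post-baseline scan, where the present schedule would have obtained one at stopping. No rule on when to stop drug changes.

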## 6. SUBJECT POPULATION

**6.1 Subject Selection and Numbers** The nature of the study and the potential risks will be explained to all candidates. Written informed consent will be obtained from each subject prior to performing any screening procedures. There will be no exemptions and subjects must satisfy all eligibility criteria in order to participate. At least 120 subjects will be enrolled.

Inclusion and exclusion criteria are to be determined at Screening unless otherwise indicated.

### 6.2 Inclusion Criteria

The criteria for entry into the study are:

1. Age  $\geq 18$  years
2. Provision of written informed consent
3. Diagnosis of NASH, histologically proven within 12 months of Screening with all of the following criteria met:
  - NASH activity score (NAS) of 4 or more
  - Cytologic ballooning score of at least 1
  - 10% or more macrovesicular steatosis
  - Hematoxylin & Eosin (H&E) stained slides and/or paraffin block available for independent assessment
4. HBA1C of  $\leq 9.0$
5. Agree to the use of effective contraceptive measures if either male or female of child bearing potential

### 6.3 Exclusion Criteria

The criteria for exclusion from the study are:

1. Presence of vascular liver disease or cirrhosis
2. Presence of liver disease from other cause (autoimmune, metabolic, medication induced)
3. BMI  $\leq 25\text{kg/m}^2$
4. Alcohol use  $\geq 30\text{g/day}$
5. Type 1 diabetes
6. History of major bariatric surgery (not including balloon / sleeve gastrectomy)
7. Weight loss or gain of 5kg or more in the past 6 months or  $\geq 10\%$  change in bodyweight in the past 12 months
8. Contraindication for MRI
9. Inadequate venous access
10. Lactating/breastfeeding/pregnant at Screening or Baseline
11. HIV antibody positive, hepatitis B surface antigen positive (HBsAg) or hepatitis C virus-RNA positive
12. Receiving an elemental diet or parenteral nutrition
13. Concurrent conditions:
  - Inflammatory bowel disease
  - Unstable angina, myocardial infarction, transient ischemic events, or stroke within 24 weeks of Screening
  - Ongoing infectious disease
  - Ongoing multi-systemic immune-mediated disease
  - Concurrent or past malignant disease
  - Any other concurrent condition which, in the opinion of the investigator, could impact adversely on the subject participating or on the interpretation of the study data

## 14. Concurrent medications including:

- Anti-NASH therapy(s) taken for more than 10 continuous days in the last 3 months. These include S-adenosyl methionine (SAM-e), betaine, milk thistle, bacterial probiotic supplements (other than yoghurt or other natural food sources), vitamin E and gemfibrozil.
  - NOTE: If determinant biopsy is performed while on stable treatment – subject is eligible;
  - Wash out for any of the anti-NASH therapies is as follow: under 10 days no washout required, more than 10 days and up to 3 months treatment requires 6 weeks washout. Any treatment of over 3 months would require to re-biopsy to ensure histological eligibility
  - Thiazolidinediones (glitazones), dipeptidyl peptidase 4 inhibitors (gliptins) or glucagon-like peptide-1 analogs in the last 6 months.  
NOTE: if determinant biopsy is performed while on stable treatment of at least 6 months – subject is eligible.
  - NOTE: Allowable anti-diabetic treatment includes metformin and/or sulfonylureas administered at constant dose for at least 2 months prior to study entry
  - NOTE: Subjects treated with Insulin are eligible if clinically stable on insulin treatment (i.e. no recurrent acute hypo-/hyperglycemic episodes diagnosed clinically and by Glucose serum levels of <50 mg/dL and >200 mg/dL respectively) for at least 2 months prior to study entry
- immune modulatory agents including:
  - Within 3 months of study entry:
    - systemic steroids for more than 7 days
    - daily treatment with multiple non-steroidal anti-inflammatory drugs (such as aspirin >100mg/day, ibuprofen, naproxen, meloxicam, celecoxib) for more than 1 month
  - In the last 12 months:
    - azathioprine, 6-mercaptopurine, methotrexate, cyclosporin, anti-TNF $\alpha$  therapies (infliximab, adalimumab, etanercept) or anti-integrin therapies (namixilab)
- more than 10 consecutive days oral or parenteral antibiotics within 4 weeks prior to study entry NOTE: subjects administered with antibiotics for more the 5 days prior to study entry would not be included in the stool and PBMC analysis)
- Variable dose of anti-lipidemic agents (HMG Co-A reductase inhibitors – “statins”) in the 3 months prior to Screening

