#### 9.2.2 During the Study Dosing Period

Throughout the study medication dosing period, subjects may not receive any of the following concomitant medications:

- other anti-NASH therapy(s) including, SAM-e, betaine, milk thistle and probiotic supplements (not including yoghurt);
- thiazolidinediones (glitazones), dipeptidyl peptidase 4 inhibitors (gliptins) or GLP-1 analogs, unless the subject was recruited on a stable dose.
- Allowable anti-diabetic treatment includes insulin, metformin and/or sulfonylureas administered at constant dose for at least 2 months prior to study entry;
- immune modulatory agents including
  - systemic steroids for more than 7 days
  - multiple non-steroidal anti-inflammatory drugs such as aspirin (>100mg/day), ibuprofen, naproxen, meloxicam, celecoxib;
  - azathioprine, 6-mercaptopurine, methotrexate, cyclosporin, anti-TNF $\alpha$  therapies (infliximab, adalimumab, etanercept) or anti-integrin therapies (namixilab).

Treatment with antilipidemic agents (HMG Co-A reductase inhibitors – “statins”), vitamin E, gemfibrozil and allowable antidiabetic treatment (metformin and/or sulfonylurea) must be stable throughout the study.

Antibiotics should be taken if clinically indicated but avoided where possible.

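### Exclusion 14 admits stable users of six anti-NASH agents, but Section 9.2.2 bans four of the six during dosing with no stable-dose exception and no rule on when to stop

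*Protocol*

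**What the plan says.** **Entry.** Protocol 6.3, exclusion 14, excludes subjects with "Anti-NASH therapy(s) taken for more than 10 continuous days in the last 3 months". It names six agents: "These include S-adenosyl methionine (SAM-e), betaine, milk thistle, bacterial probiotic supplements (other than yoghurt or other natural food sources), vitamin E and gemfibrozil". Two notes follow. The first is an exception: "NOTE: If determinant biopsy is performed while on stable treatment – subject is eligible". The second is a washout rule: "more than 10 days and up to 3 months treatment requires 6 weeks washout. Any treatment of over 3 months would require to re-biopsy". The synopsis carries the same exception and washout rule. A separate note admits users of glitazones, gliptins and GLP-1 analogs if the biopsy was done after at least 6 months of stable treatment. The biopsy may be up to 12 months before Screening (6.2).

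**Dosing period.** Protocol 9.2.2 begins "Throughout the study medication dosing period, subjects may not receive any of the following concomitant medications", and the first item is "other anti-NASH therapy(s) including, SAM-e, betaine, milk thistle and probiotic supplements (not including yoghurt". That item has no stable-dose exception. The next item, on glitazones, gliptins and GLP-1 analogs, exempts subjects recruited on a stable dose. A later paragraph covers statins and adds "vitamin E, gemfibrozil and allowable antidiabetic treatment (metformin and/or sulfonylurea) must be stable throughout the study".

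**Endpoint timing.** The primary efficacy endpoint is the change in MRI liver fat from Baseline to Week 24 (4.2). The baseline MRI comes first, and Day 0 follows within 14 days (7.2.3). The Week 24 MRI has a window of 2 weeks either side (Table 1, footnote 7).

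**Analysis.** SAP 5.4 and 5.5 tabulate prior, concomitant and new medications. SAP 7.2 has no analysis of liver fat that takes account of changed background therapy.

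**The concern.** For four agents, a subject can satisfy the entry rule and then be unable to continue the same treatment under the dosing-period rule. Either background therapy changes close to or inside the interval over which the primary endpoint is measured, or the subject breaches 9.2.2. The protocol itself treats these agents as calling for a washout or a new biopsy, so it does not regard them as inert.

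Three things are at stake. Sites may decide eligibility differently, although 6.1 allows no exemptions. The liver fat change of an affected subject may mix the effect of study drug with that of stopping another agent. And a subject admitted in good faith may later be classed as a major violator and lost from the per-protocol set (SAP 3.1), or withdrawn under Protocol 11.2.

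**Working it through.** **1. Agent-by-agent comparison**

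| Agent | Entry (6.3, exclusion 14) | Dosing period (9.2.2) | Consistent? |
|---|---|---|---|
| SAM-e | Admitted if stable at biopsy | Banned, no exception | No |
| Betaine | Admitted if stable at biopsy | Banned, no exception | No |
| Milk thistle | Admitted if stable at biopsy | Banned, no exception | No |
| Probiotics | Admitted if stable at biopsy | Banned, no exception | No |
| Vitamin E | Admitted if stable at biopsy | Allowed, must stay stable | Yes |
| Gemfibrozil | Admitted if stable at biopsy | Allowed, must stay stable | Yes |
| Glitazones, gliptins, GLP-1 analogs | Admitted if stable for 6 months at biopsy | Banned unless recruited on a stable dose | Yes for those who continue; unclear for those who stopped after biopsy |

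Four of the six named anti-NASH agents conflict.

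**2. Precedence within exclusion 14.** Take a subject with 8 months of milk thistle, biopsied on it 5 months ago and still taking it. The criterion excludes (more than 10 days in the last 3 months). The note admits (biopsied on stable treatment). The washout rule, read alone, asks for a re-biopsy (over 3 months of treatment). Now take a subject who used an agent for 5 weeks and stopped 8 weeks ago. The 6-week washout is complete, but more than 10 of the treatment days fall within the last 3 months. The text gives no order among these rules.

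**3. When stability is required.** The notes, read literally, ask for stability at the biopsy only. Section 9.2.2 speaks of the dose at recruitment. A subject biopsied on a stable GLP-1 analog who stopped before Screening meets the wording of the note, although the criterion otherwise bars these drugs for 6 months.

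**4. Timing against the MRIs.** A subject who stops at Day 0 had the baseline scan on treatment 0 to 14 days earlier, and has the Week 24 scan about 22 to 26 weeks after stopping. A subject who stops during Screening (up to 45 days) may have been off treatment for some time before the baseline scan. The documents require neither.

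**5. Size.** First the plan's own figure (Protocol 12.1): SD 6 at each time point, correlation 0.25, 40 per arm, difference 5, two-sided alpha 0.05.

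- SD of change = sqrt(2 × 6² × (1 − 0.25)) = 7.35; the protocol gives 7.3.
- Power by the noncentral t is 85.7% at SD 7.3 and 85.2% at 7.35. The stated figure of about 85% reproduces.

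The documents give neither the share of subjects who would stop (p) nor the effect of stopping on liver fat change (d). For illustration only, assume p of 5% to 20% and d of 2 to 5 points, the same in every arm.

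- SD = sqrt(7.3² + p(1 − p)d²). Lowest: sqrt(53.29 + 0.0475 × 4) = 7.31, power 85.5%. Highest: sqrt(53.29 + 0.16 × 25) = 7.57, power 83.1%.
- Expected shift in each arm's mean = p × d: 0.05 × 2 = 0.1 to 0.20 × 5 = 1.0 point. It is the same in all arms, so it cancels in the contrast with placebo.
- Chance imbalance between two arms (1 SD) = d × sqrt(2p(1 − p)/40): 2 × sqrt(0.002375) = 0.10 to 5 × sqrt(0.008) = 0.45 point, against a planned effect of 5.
- SAP 7.2 also tests within four fat-fraction categories. If these were equal in size (assumed; 10 per arm per category), the imbalance doubles to about 0.19 to 0.89 point.

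**The case against.** The strongest defence is that exclusion 14 can be read in order: a general bar, an exception for those biopsied on stable treatment, and a washout or re-biopsy route for everyone else. The stated purpose of the re-biopsy is histological eligibility, which a biopsy taken on treatment arguably serves already. The reference in 9.2.2 to subjects recruited on a stable dose likewise suggests that the glitazone-class note is meant for continuing users. These readings are reasonable and may be what was intended. But the text does not state them, and none of them removes the conflict with 9.2.2 for the four agents.

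It can also be said that the harm is small. Subjects who breach 9.2.2 stay in the FAS, the protocol's primary efficacy set. The medical monitor judges major violations before unblinding. Withdrawal under 11.2 is discretionary, and unnecessary withdrawal is to be avoided. All of this stands: per-protocol exclusion and withdrawal are possible, not automatic.

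Three stronger readings are tempting, and the documents do not support them:

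- That 9.2.2 bans everything exclusion 14 admits. Vitamin E and gemfibrozil may continue if stable, and the three antidiabetic classes have a stable-dose exception.
- That every affected subject is scanned on therapy at baseline and off it at Week 24. This is likely for someone who stops only when the ban begins. A subject could also stop earlier in Screening, or continue as a deviation.
- That the trial is biased against the drug. Any shift from stopping is expected equally in the placebo arm.

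**Conclusion.** The contradiction is established from the text for SAM-e, betaine, milk thistle and probiotics, and no other section resolves it. The unstated precedence within exclusion 14 and the unstated time at which stability is required are related ambiguities of lesser weight.

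For the active-placebo comparison, the consequence is added noise, chance imbalance and possible per-protocol exclusions, not systematic bias. Its size cannot be derived from the documents. On the assumed ranges above, the loss of power is at most about 2.6 points (85.7% to 83.1%), so the stated power is not seriously threatened. The main cost is inconsistent eligibility decisions and individual liver fat changes that are hard to interpret. The plan should be corrected, but the point does not undermine the primary analysis.

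**What to change.** **Protocol.** Reconcile 6.3 exclusion 14, its synopsis copy and 9.2.2, so that each listed agent has one consistent status from entry through Week 24. State which rule prevails among the criterion, the stable-treatment note and the washout or re-biopsy rule. State the time at which stability is required. Which agents are allowed, and on what terms, is for the sponsor's clinical team.

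**SAP 7.2.** Add one sensitivity analysis of change in liver fat that leaves out subjects whose listed anti-NASH or glucose-lowering therapy was started, stopped or changed shortly before the baseline MRI or between it and the Week 24 MRI. Fix the length of the look-back before unblinding. Report the number left out by arm: changes after randomisation may depend on treatment, so this analysis supports the main one and does not replace it.

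**Cost.** A protocol clarification and one extra analysis. A few subjects' eligibility may change. NASH medication history, concurrent medication and changes during the study are already recorded (Protocol 7.3.1 and Section 9). Neither section mentions start and stop dates, so confirm that the CRF captures them.
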